6.2.3.3. ANCOVA Analysis using Actual Stratification Factors

The primary ANCOVA analysis will be repeated as a sensitivity analysis using the actual stratification factors in the model. This sensitivity analysis will be performed on the double-blind mITT analysis set.

6.2.3.4. Analysis Split by Treatment Regimen Group

A sensitivity analysis will be performed on the primary estimand to assess the sensitivity of the analysis to treatment regimen. This analysis will be identical to the primary analysis but where the two fremanezumab treated groups will be presented separately. The columns will be placebo, TEV-48125 225 mg monthly and TEV-48125 675 mg quarterly and the treatment comparisons will be TEV-48125 225 mg monthly – placebo and TEV-48125 675 mg quarterly – placebo. For both the individual treatment groups and the treatment comparisons the LS mean, SE and corresponding 95% confidence interval will be presented. No p-values will be presented for this additional analysis.

6.2.4. Supplementary Estimands

A supplementary estimand will estimate treatment effect in the hypothetical scenario where no one early terminates from study drug. The estimand is the difference in adjusted means between fremanezumab group and placebo group in the population that comprises the patients in the double-blind mITT analysis set for the change from baseline in the monthly average number of migraine days during the 12-week period after the 1st dose of IMP where the ICEs are handled as per Table 2.

Intercurrent event	Strategy
Patient early terminates from the IMP	Hypothetical: For patients in the monthly dosing regimen group who early terminate from study drugs, observations collected more than 4 weeks after the last dose will be treated as missing. In formula (1) an average is taken so these values which are left missing due to early termination will be replaced with the average for that month of those in the same treatment group who do not early terminate. Missing observations prior to early termination will not be replaced.
Patient receives the wrong IMP due to medication errors	Treatment policy ¹

Table 2: Intercurrent Event Strategies: 1st Supplementary Estimand

Intercurrent event	Strategy
Patient receives a rescue medication due to	Treatment policy ¹
worsening symptoms	

¹Treatment policy: if observations are collected after the occurrences of the ICEs, the observations will be included in the calculation of the primary endpoint for the primary analysis.

A second supplementary estimand will estimate treatment effect in the hypothetical scenario where no one takes rescue medication (rescue medication is indicated by a response of Yes to C1 or C3, and a medication present in response to C2 of the electronic headache diary device). A rescue medication for migraine is defined as medication that does not abort a migraine, but masks the pain for a few hours until the migraine runs its course.

The estimand is the difference in adjusted means between fremanezumab group and placebo group in the population that comprises the patients in the double-blind mITT analysis set for the change from baseline in the monthly average number of migraine days during the 12-week period after the 1st dose of IMP where the ICEs are handled as per Table 3.

Table 3: Intercurrent Event Strategies: 2 nd Suppl	lementary Estimand
---	--------------------

Intercurrent event	Strategy
Patient early terminates from the IMP	Treatment policy ¹
Patient receives the wrong IMP due to medication errors	Treatment policy ¹
Patient receives a rescue medication due to worsening symptoms	Hypothetical: For patients who start a rescue medication, observations collected after starting rescue medication will be treated as missing. In formula (1) an average is taken so these values which are left missing due to starting rescue medication will be replaced with the average for that month of those in the same treatment group who do not start rescue medication.

¹Treatment policy: if observations are collected after the occurrences of the ICEs, the observations will be included in the calculation of the primary endpoint for the primary analysis.

A third supplementary estimand will estimate treatment effect in the population that comprises the patients in the ITT analysis set. The estimand is the difference in adjusted means between fremanezumab group and placebo group for the change from baseline in the monthly average number of migraine days during the 12-week period after the 1st dose of IMP where the ICEs are handled as per Table 1.

Finally, a fourth supplementary estimand will estimate the treatment effect in the population that comprises the patients in the PP analysis set. The estimand is the difference in adjusted means between fremanezumab group and placebo group for the change from baseline in the monthly average number of migraine days during the 12-week period after the 1st dose of IMP where the relevant ICE is handled as per Table 4.

Table 4: Intercurrent Event Strategies: 4 th Supplementary Estimand	

Intercurrent event	Strategy
Patient receives a rescue medication due to	Treatment policy ¹
worsening symptoms	

¹Treatment policy: if observations are collected after the occurrences of the ICEs, the observations will be included in the calculation of the primary endpoint for the primary analysis.

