| 
Any patient should be excluded if any suicidal behaviors are reported suicide attempt in the past, suicidal ideation with a specific plan in the past 2 years prior to screening (visit 1), or current suicidal ideation will result in patient exclusion.
 
Any patient with lifetime suicidal behaviors (actual, interrupted, and aborted attempts and preparatory actions) and current suicidal ideation should be excluded and/or discontinued from study treatment. Investigators will inquire about and evaluate suicidal ideation, plan, and behavior based on their clinical judgement and refer patients to psychiatric care as appropriate.
 | 
Any suicide attempt in the past, suicidal ideation with a specific plan in the past 2 years prior to screening (visit 1), or current suicidal ideation will result in patient exclusion.
 
Investigators will inquire about and evaluate suicidal ideation, plan, and behavior based on their clinical judgement and refer patients to psychiatric care as appropriate.
 | 
Clarified the assessment of suicidality that will result in patient exclusion
 | |
| Section 9.1 Sample Size and Power Considerations | | | |
| 
Therefore, the sample size and power estimation were conducted, assuming that the treatment difference between fremanezumab and placebo is 1.6 days (common SD 4.45 days).
 
To ensure adequate representation of patients with both migraine types (EM and CM), the enrollment minimum of either migraine type is 30%. In addition, primary efficacy analysis will be stratified by EM and CM and subgroup analysis for EM and CM will be conducted.
 | 
Therefore, the sample size and power estimation were conducted, assuming that the treatment difference between fremanezumab and placebo is 1.6 days (common SD 4.45 days).
 
To ensure adequate representation of patients with both migraine types (EM and CM), the enrollment minimum of either migraine type is 30%. In addition, primary efficacy analysis will be stratified by EM and CM and subgroup analysis for EM and CM will be conducted.
 | 
Clarified enrollment minimums for each migraine type
 | |
| Appendix A CLINICAL LABORATORIES AND OTHER DEPARTMENTS AND INSTITUTIONS | | | |

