2.4. Sample Size and Power Considerations

Using study data from 2 completed Phase 3 US pivotal studies in migraine, it is estimated that 163 completers per treatment group (ie, combined fremanezumab groups and placebo group) will provide at least 90% power to detect the assumed treatment difference at a significance level of 0.05. Assuming a 12% discontinuation rate, approximately 372 patients will be randomized in this study (93 patients in each fremanezumab treatment group and 186 patients in the placebo group). The primary efficacy analysis will consider all fremanezumab-treated patients as 1 group.

To ensure adequate representation of patients with both migraine types (EM and CM), the enrollment minimum of either migraine type is 30%. In addition, primary efficacy analysis will be stratified by EM and CM, and subgroup analysis for EM and CM will be conducted.

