6. EFFICACY ANALYSIS

6.1. General

For the purposes of this study;

- CM is defined as headache occurring on ≥ 15 days during the screening period.
- EM is defined as headache occurring on <15 days during the screening period.

All e-diary data collected during the screening period, regardless of the duration beyond 28 days (e.g., 30 days), will be included and analyzed. There will be no exclusion of any e-diary data during the screening period.

A migraine day is endorsed when at least one of the following situations occurs:

- A calendar day (0:00 to 23:59) demonstrating at least 2 consecutive hours of a headache meeting the criteria for migraine with or without aura
- A calendar day (0:00 to 23:59) demonstrating at least 2 consecutive hours of a headache meeting the criteria for probable migraine, a migraine subtype where only 1 migraine criterion is missing
- A calendar day (0:00 to 23:59) demonstrating a headache of any duration that was treated with migraine-specific medications (triptans and ergot compounds)

A headache day of at least moderate severity is endorsed when at least 1 of the following situations occurs:

- a calendar day (0:00 to 23:59) demonstrating at least 2 consecutive hours of headache of at least moderate severity
- a calendar day (0:00 to 23:59) demonstrating a headache of any duration that was treated with migraine-specific acute medications (triptans and ergot compounds)

The derivation logic for both migraine day and headache day of at least moderate severity is presented in Appendix B.

In addition, a headache day of any severity is endorsed when at least 1 of the following situations occurs:

- a calendar day (00:00 to 23:59) demonstrating at least 2 consecutive hours of headache of any severity
- a calendar day (0:00 to 23:59) demonstrating a headache of any duration that was treated with migraine-specific acute medications (triptans and ergot compounds)

The endpoint of headache hours of at least moderate severity is obtained directly from the corresponding electronic headache diary device question (Question A5).

The endpoint of days of use of any acute headache medication is obtained directly from the corresponding electronic headache diary device questions (Question C1=Yes or C3=Yes and C2 has a medication present).

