6.2.2. Primary Analysis of the Primary Estimand

The hypothesis testing for the primary analysis is:

 $H_o: \delta_1 = \delta_2$ vs $H_a: \delta_1 \neq \delta_2$

where δ_1 and δ_2 are the parameters of mean change from baseline in the monthly average number of migraine days during the 12-week period after the 1st dose of IMP for the combined TEV-48125 treatment groups and the placebo group respectively.

An analysis of covariance (ANCOVA) will be performed, including treatment (combined TEV-48125 groups vs. placebo) and stratification factors (as randomized) of migraine type (CM vs EM) and baseline preventive medication use (yes vs no) as fixed factors, as well as baseline number of migraine days as a covariate in the model. For the individual treatment groups (combined TEV-48125 groups and placebo) the least square (LS) mean, standard error (SE) and corresponding 95% confidence interval will be presented. For the treatment difference (combined TEV-48125 groups - placebo) the LS mean, SE, corresponding 95% confidence interval and p-value for comparison will be presented.

The statistical test will be two-sided at the alpha = 0.05 level of significance. Model fitting assumptions will be investigated.

Example SAS code is provided in Appendix D.

A hierarchical procedure will be used to control the type 1 error rate, as described in Section 7.

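### The second supplementary estimand (SAP 6.2.4) defines rescue medication in two incompatible ways, and its censor-and-fill rule gives an uninterpretable, falsely precise estimate

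*SAP*

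**What the plan says.** The second supplementary estimand in SAP 6.2.4 targets the effect if nobody took rescue medication. Three statements identify the event:

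- Diary flag: "rescue medication is indicated by a response of Yes to C1 or C3, and a medication present in response to C2".
- Verbal definition, in the following sentence: "A rescue medication for migraine is defined as medication that does not abort a migraine, but masks the pain for a few hours".
- Table 3 label: rescue received because symptoms worsened.

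Once the event occurs, Table 3 sets all later observations to missing, with no resumption. Those values are "replaced with the average for that month of those in the same treatment group who do not start rescue medication". SAP 6.2.5 then applies the primary ANCOVA of 6.2.2 unchanged, so a confidence interval and p-value will be reported.

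SAP 6.1 uses the same diary logic for a different variable: "The endpoint of days of use of any acute headache medication is obtained directly from the corresponding electronic headache diary device questions", namely C1 or C3 answered Yes with a medication in C2. That variable is a secondary endpoint. Protocol 5.6 lets patients treat breakthrough attacks as needed. Protocol 6.1.1 lists opioids, barbiturates, triptans, ergots, NSAIDs, acetaminophen and combinations as the acute drugs to be recorded.

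**The concern.** The flag and the definition describe different events. The flag has no drug-class filter, so a triptan taken for an ordinary attack counts as rescue. The medication items in SAP Appendix A (C1 to C3) ask whether and which medication was taken, not whether it aborted the attack or whether symptoms had worsened.

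Two consequences follow. First, one ordinary acute dose removes the rest of that patient's diary. Second, the patients left to supply the fill-in means are selected on the outcome. In SAP Appendix B, Options 2 and 3 for a migraine day require an ergot or triptan entry, or a non-prescription entry with a C2 medication, and both trip the flag. An unflagged patient therefore cannot have a migraine day by either route, whereas baseline values keep all such days. A constant is then imputed for most of the data and analysed as if observed. At stake is a supplementary result that may disagree with the primary one, or appear to confirm it strongly, for reasons unrelated to rescue.

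**Working it through.** **Inputs from the documents.** Alpha: "The statistical test will be two-sided at the alpha = 0.05 level of significance" (SAP 6.2.2). Size: "163 completers per treatment group (ie, combined fremanezumab groups and placebo group) will provide at least 90% power" and "Assuming a 12% discontinuation rate, approximately 372 patients will be randomized" (SAP 2.4). The difference of 1.6 days and SD of 4.45 days are legible only in the amendment log (Protocol 16.4), because the current text is redacted. Eligibility needs at least 4 baseline migraine days (Protocol 4.1, criterion g). Placebo improvement of 2.6 days comes from the earlier episodic-migraine study (Protocol 1.2.2.2).

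**The plan's own figure.** n = 2(1.960 + 1.282)² × (4.45/1.6)² = 2 × 10.51 × 7.735 = 162.6, so 163 per group (power 90.1%). 163/0.88 = 185.2, so 186 per arm and 372 in total. This reproduces the plan. The SAP gives no figure for the number flagged or for this estimate.

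**Chance of escaping the flag.** With m migraine days per 28, a share p of them medicated, and independent days, P(no flag in 84 days) = (1 − mp/28)^84.

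- m = 4, p = 0.5: (1 − 2/28)^84 = 0.2%
- m = 4, p = 0.3: (1 − 1.2/28)^84 = 2.5%
- m = 8, p = 0.3: (1 − 2.4/28)^84 = 0.05%
- m = 1, p = 0.5: (1 − 0.5/28)^84 = 22%

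Among patients who medicate at all, those who escape are mostly those with very few migraine days.

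**Simulation of the Table 3 rule.** 186 per arm, daily diaries, 200–300 runs, ANCOVA on treatment, migraine type and baseline, true effect −1.6. Assumptions not in the documents: mean baseline about 10–12 migraine days, 30–50% chronic migraine, SD of change 4.0, p from 0.5 to 0.9, and a share q of 0–30% of patients who never medicate. Results for p = 0.75 and 50% chronic migraine, with the reference group read as patients never flagged in 12 weeks:

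| q | Flagged, placebo / active | Primary estimate | Table 3 estimate | Run-to-run SD | Model SE |
|---|---|---|---|---|---|
| 0 | 92.7% / 87.1% | −1.52 | −0.03 | 0.04 | 0.03 |
| 2% | 90.5% / 85.3% | −1.48 | −0.93 | 1.30 | 0.14 |
| 5% | 87.7% / 83.2% | −1.43 | −1.53 | 1.62 | 0.20 |
| 10% | 82.9% / 78.2% | −1.46 | −1.80 | 1.26 | 0.26 |
| 20% | 74.5% / 69.8% | −1.49 | −1.96 | 1.11 | 0.32 |
| 30% | 64.3% / 61.2% | −1.45 | −1.89 | 1.07 | 0.36 |

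The primary SE is 0.41 throughout. The placebo reference group is about 186 × (1 − 0.927) = 14 patients at q = 0 and 186 × (1 − 0.877) = 23 at q = 5%.

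Over all settings, 58–93% of patients are flagged and the median first flag falls on day 3–18, so most of the 84 days are fill-in values. The estimate is −0.02 to −0.11 at q = 0, −0.9 to −1.5 at q = 5%, −1.3 to −1.8 at q = 10%, and −1.6 to −2.0 at q = 20–30%. Dropping the first treated day takes the q = 10% result to −2.1. Reading the reference group as patients not yet flagged by the end of each month changes little.

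**No true effect.** The nominal 5% test rejects in 25–56% of runs at q = 0 and 60–81% at q = 5–20%.

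A second simulation of the same rule agrees: −0.19 against a primary estimate of −1.45 when every patient medicates some attacks, −1.5 to −1.8 with 5–20% never medicating, model SE 0.08–0.31 against a run-to-run SD of 0.4–1.5, and 61–79% false rejection.

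**The case against.** A reader might infer that almost every patient is censored and that the estimate must collapse to zero and contradict the primary result. The documents do not support that. They give no acute-medication rate, and the near-zero result needs essentially every patient to medicate some attacks. Patients who are never flagged are possible: herbal medicine and acupuncture are permitted (Protocol 5.6) but are not among the acute drugs listed for the diary. With 10% or more such patients, the estimate is near or beyond the primary one.

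A reader might also take the verbal definition as correct and the flag as the mistake. Protocol 5.3.2 treats acute and rescue medication as the same thing, so the verbal definition may be the stray sentence. The text supports only a request to reconcile them. Accepting the flag does not save Table 3, however, because it makes the event ordinary acute treatment.

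A class filter alone may not suffice: with triptans and ergots removed, NSAIDs and acetaminophen could still flag most patients. The simulation also left out the preventive-medication factor.

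Finally, the reach is limited. This is one of four supplementary estimands, outside the hierarchy in SAP Section 7. Table 1 handles rescue by treatment policy, the MMRM and multiple-imputation sensitivity analyses do not use the flag, and Protocol 9.5.4.2 made the related analysis optional. All of this stands. It limits the severity but does not make the reported interval or p-value valid.

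**Conclusion.** The point holds for this one analysis. The contradiction is in the text and needs no assumption. That a large majority would be flagged early is an inference from assumed use rates (58–93%). The direction of the bias is not determined: the estimate is near zero if essentially all patients medicate some attacks, and otherwise may match or exceed the primary estimate. The sturdier defect is false precision. At q = 5–20% the model SE is 0.18–0.33 against a run-to-run SD of 0.8–1.6, and false rejection is roughly 25–80% across the null settings. If an arm-month had no unflagged patient, the rule could not be computed at all. The primary estimand, sample size and alpha are unaffected.

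**What to change.** In SAP 6.2.4 and Table 3:

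1. Reconcile the two sentences and the Table 3 label into one definition, and derive the event from the C2 drug name or class to match it. SAP 6.1 already filters C2 for triptans and ergots, so this can be programmed. Leave ordinary acute medication under treatment policy, as in Table 1.
2. State whether the first flagged day is kept.
3. Replace the single arm-by-month mean with multiple imputation conditional on baseline, strata and observed months within randomized arm. The 6.2.3.2 procedure can be adapted but not used unchanged: it runs in the ITT set and reassigns some active-arm patients to placebo, whereas this estimand is in the mITT set and needs no reassignment. Imputation carries the missing-data uncertainty into the SE, but it does not cure the selection caused by an over-broad flag, so step 1 must come first.
4. If the diary cannot separate rescue from ordinary acute use, delete this estimand.

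The cost is SAP wording and reprogramming of one supplementary analysis. No new data are needed, and nothing changes in what patients may take.

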6.2. Primary Efficacy Endpoint and Analysis

6.2.1. Primary Estimand

The primary estimand will be the difference in adjusted means between fremanezumab group and placebo group in the population that comprises the patients in the double-blind mITT analysis set for the change from baseline in the monthly average number of migraine days during the 12-week period after the 1st dose of IMP. The intercurrent events (ICEs) that may affect the efficacy endpoint will be handled as per Table 1.

Intercurrent event	Strategy
Patient early terminates from the IMP	Treatment policy ¹
Patient receives the wrong IMP due to medication errors	Treatment policy ¹
Patient receives a rescue medication due to worsening symptoms	Treatment policy ¹

Table 1: Intercurrent Event Strategies: Primary Estimand

¹Treatment policy: if observations are collected after the occurrences of the ICEs, the observations will be included in the calculation of the primary endpoint for the primary analysis.

The baseline values will be derived using formula (3). The post baseline values will be derived using formula (1), and *the change* is calculated as *postbaseline – baseline value*.

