6.2.3.2. Analysis with Multiple Imputation Method

Multiple imputation (MI) method will be applied to impute the monthly missing data assuming a missing not at random (MNAR) mechanism. The data will be processed by the following steps.

- If a patient has <10 days of electronic headache diary device data in a month, that month's value will be considered missing before the MI procedure.
- For the patients in the active treatment groups who are early terminated with reasons of treatment-related adverse event or lack of efficacy, they will be assigned to placebo group so their missing values will be imputed using data from the placebo treated patients.
- Run SAS PROC MI procedure to create 100 complete datasets.
- Within each imputed data set, for a patient who has partial, say X days (X<28), electronic headache diary device data in a month, the monthly value will be replaced by ∑(oberseved migraine days) + (28 X) * imputed value/28
- The monthly average number of migraine days *during the 12-week period* after the 1st dose of study drug will be the average of month 1, month 2, and month 3 values.

Each dataset will be analyzed using the same ANCOVA model as described in Section 6.2.2. The LS means and standard errors from each analysis will be output to a SAS data set. SAS MIANALYZE procedure will be used to generate the final LS means (\pm SE) for the treatment groups and the treatment difference (TEV-48125 - placebo) as well as p-values associated with

treatment differences. The 95% confidence intervals for the treatment difference will also be constructed.

The output dataset will contain the estimate of the mean difference and the standard error of the estimate from each of the 100 datasets. SAS procedure, PROC MIANALYZE, will be used to generate an overall p-value and 95% CI for the treatment difference.

This sensitivity analysis will be performed on the ITT analysis set.

Example SAS code is provided in Appendix D.

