6.2.5. Analysis of the Supplementary Estimands

The supplementary estimands will be analyzed using the same methods as the primary estimand, as detailed in Section 6.2.2.

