APPENDIX D. EXAMPLE SAS CODE

The following sample SAS code pertains to the primary efficacy ANCOVA analysis:

ODS OUTPUT DIFFS = XXX LSMEANS = XXX

PROC MIXED DATA = XXX;

CLASS TREATMENT MIGRAINETYPE PREVENTIVEMEDICATION;

MODEL CHG = TREATMENT MIGRAINETYPE PREVENTIVEMEDICATION BASE;

LSMEANS TREATMENT / CL PDIFF;

RUN;

The following SAS code pertains to the main MMRM analysis:

ODS OUTPUT DIFFS = XXX LSMEANS = XXX

PROC MIXED DATA=XXX;

CLASS USUBJID MONTH TREATMENT MIGRAINETYPE PREVENTIVEMEDICATION;

MODEL CHG=BASE MONTH TREATMENT MIGRAINETYPE PREVENTIVEMEDICATION TREATMENT*MONTH;

REPEATED MONTH/SUBJECT=USUBJID TYPE=UN;

LSMEANS TREATMENT TREATMENT*MONTH/PDIFF CL ALPHA=0.05;

RUN;

The following SAS code pertains to the sensitivity MMRM analysis:

ODS OUTPUT DIFFS = XXX LSMEANS = XXX

PROC MIXED DATA=XXX;

CLASS USUBJID MONTH TREATMENT MIGRAINETYPE PREVENTIVEMEDICATION;

MODEL CHG=BASE MONTH TREATMENT MIGRAINETYPE PREVENTIVEMEDICATION TREATMENT*MONTH BASE*MONTH;

REPEATED MONTH/SUBJECT=USUBJID TYPE=UN;

LSMEANS TREATMENT TREATMENT*MONTH/PDIFF CL ALPHA=0.05;

RUN;

The following SAS code pertains to the MI analysis:

PROC MI DATA=XX SEED=98765 OUT=MI_OUT NIMPUTE=100 MAXIMUM=... 28 28 28 MINIMUM=... 0 0 0 0;

CLASS TRTMI MIGRAINETYPE PREVENTIVEMEDICATION;

FCS REG(V0=TRTMI MIGRAINETYPE PREVENTIVEMEDICATION /DETAILS) NBITER=100;

FCS REG(V1=TRTMI MIGRAINETYPE PREVENTIVEMEDICATION V0 /DETAILS) NBITER=100;

FCS REG(V2=TRTMI MIGRAINETYPE PREVENTIVEMEDICATION V0 V1/DETAILS) NBITER=100;

FCS REG(V3=TRTMI MIGRAINETYPE PREVENTIVEMEDICATION

V0 V1 V2/DETAILS) NBITER=100; VAR TRTMI MIGRAINETYPE PREVENTIVEMEDICATION V0 V1 V2 V3;

RUN;

where TRTMI is the placebo reassigned treatment group.

The output dataset from the below SAS code will contain the estimate of the mean difference and the standard error of the estimate from each of the 100 datasets

ODS OUTPUT DIFFS=DIFF LSMEANS=LSM; PROC MIXED DATA=UPDATED_MI_OUT METHOD=REML; BY IMPUTATION; CLASS TREAT MIGRAINETYPE PREVENTIVEMEDICATION; MODEL CHG=BASE TREAT MIGRAINETYPE PREVENTIVEMEDICATION; LSMEANS TREAT/DIFF;

RUN;

where TREAT is the planned randomized treatment group.

SAS PROC MIANALYZE code is as follows;

ODS OUTPUT PARAMETERESTIMATES=PARMEST; PROC MIANALYZE DATA=MIXED_OUT ALPHA=0.05 THETA0=0; BY TREAT; MODELEFFECTS ESTIMATE; STDERR STDERR;

RUN; where TREAT is the planned randomized treatment group.

The following SAS code pertains to the logistic regression analysis:

PROC LOGISTIC DATA = XXX;

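### SAP 6.2.4, Table 3: filling post-rescue diary days with one arm-by-month mean and running the ordinary ANCOVA makes the reported SE too small

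*SAP*

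**What the plan says.** SAP 6.2.4 defines a hypothetical estimand in which nobody takes rescue medication. Under Table 3, every diary observation after rescue starts is treated as missing. In the 12-week formula each such value "will be replaced with the average for that month of those in the same treatment group who do not start rescue medication". Section 6.2.5 adds: "The supplementary estimands will be analyzed using the same methods as the primary estimand". Those methods are the ANCOVA of 6.2.2, which reports an LS mean difference, SE, 95% confidence interval and p-value. No variance adjustment is specified.

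For a different sensitivity analysis the same SAP does carry imputation uncertainty. Section 6.2.3.2 creates 100 imputed data sets, after which "SAS procedure, PROC MIANALYZE, will be used to generate an overall p-value and 95% CI for the treatment difference".

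The event that triggers the rule is described in several ways:

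- **Diary flag (6.2.4):** "rescue medication is indicated by a response of Yes to C1 or C3, and a medication present in response to C2". Section 6.1 uses the same items for days with any acute headache medication: "Question C1=Yes or C3=Yes and C2 has a medication present".
- **Verbal definition (6.2.4, next sentence):** "A rescue medication for migraine is defined as medication that does not abort a migraine, but masks the pain for a few hours". No drug list is attached.
- **Event label (Tables 1 to 4; similar wording in protocol 9.5.4.1):** "Patient receives a rescue medication due to worsening symptoms". No diary question in SAP Appendix A records worsening.
- **Protocol 5.3.2:** treats acute and rescue medication as the same thing, allowed for breakthrough episodes.

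**The concern.** This is single mean imputation. Filled patients become nearly identical within their arm, so the residual variance shrinks, while the model still counts the full number of patients as observed. Both effects push the SE down. The more rescue medication is used, the more data are discarded and the more precise the result appears.

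This analysis exists to show whether the primary result depends on rescue use, and its interval would mislead on exactly that point. The size depends on f. Under the broad flag, one treated headache in 12 weeks flags a patient permanently, in a population with at least 4 migraine days at baseline and acute medication allowed as needed. f could then be small. A narrower, drug-based reading would give a larger f and a smaller error.

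**Working it through.** **1. Inputs, and the plan's own figure.** Difference 1.6 days and SD 4.45 days appear only in the protocol's summary of changes for Section 9.1 (Amendment 01); the current text is redacted. They reproduce the stated sample size: n = 2 × (1.960 + 1.282)² × (4.45/1.6)² = 162.6, so 163 per group. Then 163/0.88 = 185.2, so 186 per group and 372 in total. The SD and group size are therefore consistent with the plan.

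**2. Ceiling.** Suppose flagged patients are filled for almost all 84 days. Per arm, the filled data have variance about f·s², so the model uses f·s²/n. The arm mean is really the donor mean, with variance s²/(f·n). Hence

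true SE / reported SE = √[(2s²/(f·n)) / (2f·s²/n)] = 1/f,

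or 1/√(f₁f₀) if the arms differ. With s = 4.45 and n = 186:

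| f | Reported SE = s√(2f/n) | True SE = s√(2/(fn)) | Ratio |
|---|---|---|---|
| 0.9 | 0.438 | 0.486 | 1.11 |
| 0.7 | 0.386 | 0.552 | 1.43 |
| 0.5 | 0.326 | 0.653 | 2.0 |
| 0.3 | 0.253 | 0.842 | 3.3 |

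**3. Simulation of the rule as written.** Patients keep their own days up to first use, so the actual ratio is usually below 1/f. Set-up: 1000 trials per scenario, 186 per arm, 84 daily entries, no treatment effect, and ANCOVA on arm and baseline. Assumptions: mean baseline 10.45 migraine days, SD of change 4.46, donors never flagged over 12 weeks, combined fremanezumab arm.

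- Pattern A (early first use): 30%, 55%, 75% or 90% of patients are users and medicate 60% of migraine days.
- Pattern B (later first use; never-users mainly have few migraine days): each patient's chance of medicating a migraine day follows Beta(0.1, 0.9), (0.45, 4.05), (1.3, 11.7) or (2, 8).

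| Pattern | f | Days replaced | Reported SE | True SD | Ratio | 1/f (unrounded f) | Null rejection |
|---|---|---|---|---|---|---|---|
| A | 0.70 | 27% | 0.391 | 0.538 | 1.4 | 1.4 | 0.14 |
| A | 0.45 | 50% | 0.333 | 0.715 | 2.1 | 2.2 | 0.36 |
| A | 0.25 | 68% | 0.266 | 1.017 | 3.8 | 3.9 | 0.62 |
| A | 0.10 | 81% | 0.187 | 1.613 | 8.6 | 9.6 | 0.83 |
| B | 0.69 | 24% | 0.388 | 0.537 | 1.4 | 1.5 | 0.15 |
| B | 0.44 | 40% | 0.328 | 0.599 | 1.8 | 2.3 | 0.28 |
| B | 0.29 | 50% | 0.271 | 0.660 | 2.4 | 3.5 | 0.41 |
| B | 0.12 | 68% | 0.182 | 0.928 | 5.1 | 8.6 | 0.69 |

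ANCOVA on the complete diary gave SE 0.435 to 0.437 and null rejection 0.039 to 0.064. All eight Table 3 SEs are smaller than that, although 24% to 81% of days had been replaced.

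**4. Does multiple imputation repair the SE?** Same scenarios, with sequential regression on randomized arm, baseline and earlier months. Months with fewer than 10 days were imputed and combined by the 6.2.3.2 partial-month formula, with 20 imputations and Rubin's rules. SE was 0.465 to 0.715 against true SD 0.475 to 0.717; null rejection was 0.042 to 0.064.

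**5. No donors.** The chance that at least one arm of 186 has no unflagged patient is 1 − [1 − (1 − f)¹⁸⁶]²: 0.90 at f = 0.2%, 0.28 at 1% and 0.05 at 2%. The replacement mean is then undefined.

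**6. Table 2 (early termination).** The same fill applies to the monthly regimen. At 12% discontinuation, f = 1 − 0.12 × 93/186 = 0.94 in the combined arm, and √[(1/0.94 + 1)/(0.94 + 1)] = 1.03. If placebo is also covered at f = 0.88, √[(1/0.94 + 1/0.88)/(0.94 + 0.88)] = 1.10. Both are ceilings, because data up to 4 weeks after the last dose are kept.

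**The case against.** **Low consequence.** The estimand is supplementary, the primary estimand uses treatment policy, and SAP Section 7 leaves this analysis out of the testing sequence. That stands. The rejection rates above describe this interval and are not the trial's type 1 error.

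**The multiples rest on assumed inputs.** This also stands. f, the baseline mean and the medication patterns are not in the documents. The direction of the error is certain; its size is illustrative.

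**The donor group can be read differently.** Donors might be patients who have not started rescue by the end of that month. In a second daily-diary simulation this changed little: 1.90 against 1.92 at f = 0.5, and 2.29 against 2.47 at f = 0.28. If "treatment group" means the three randomized groups (93/93/186), the no-donor chances rise to about 0.99, 0.69 and 0.30.

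**Worsening might be found outside the diary.** Protocol 5.6 records concomitant medication with indication and dates. The SAP, however, ties the flag to diary items only.

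**Multiple imputation does not cure donor selection.** This is the most substantial point. With an assumed 1.6-day shift, selective never-users and f about 0.23, the estimate moved from −1.36 on the full diary to −0.69 under Table 3 and −1.21 under imputation. With early use and f about 0.19, imputation gave −0.97 against −1.34, with coverage about 0.85. At larger f (0.35 to 0.74 with early use, plus later-use cases), imputation covered 0.935 to 0.962 under no effect and 0.918 to 0.955 under a 1.6-day effect, against 0.54 to 0.89 for Table 3. So imputation is clearly better but not a full remedy at low f, and fixing the event definition matters as much.

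**Conclusion.** The concern holds. As written, the Table 3 analysis understates its SE whenever any patient is flagged, by a factor of up to about 1/f. The factor is near 1.4 if about 70% of patients are never flagged, about 2 if 45% are, and 5 or more if only about 10% are. These multiples depend on f, on when first use occurs and on the simulation assumptions. With later use they fall well below 1/f. f cannot be judged from the documents, because the flag, the verbal definition and the event label do not describe one programmable event. The effect on Table 2 is minor (at most 1.03 to 1.10). The primary analysis, alpha control and sample size are not affected. The change should be made, but it does not threaten the trial's main conclusion.

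**What to change.** 1. **Table 3, and Table 2 for consistency:** replace the arm-mean fill with multiple imputation in the double-blind mITT set by randomized group, combined with PROC MIANALYZE. The Appendix D code can be adapted. There, "where TRTMI is the placebo reassigned treatment group"; here TRTMI should be the randomized arm, without the placebo reassignment of 6.2.3.2. State that this corrects the SE but not donor selection.
2. **Before the first interim lock, while blinded:** reconcile the descriptions of rescue medication in SAP 6.2.4, SAP Tables 1 to 4 and protocol 5.3.2 and 9.5.4.1 into one programmable event, with a C2 drug list if a drug filter is intended. Check the blinded pooled share of patients flagged.
3. **Minor clarification:** say whether the Table 2 rule for the monthly regimen also covers placebo.
4. **Optional:** list in SAP Section 14 that protocol 9.5.4.2 left such data out of the calculation, whereas the SAP fills them.

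Cost: SAP wording, one blinded count and a small edit to existing code. The intervals for the two supplementary analyses become wider (for Table 3, simulated SE 0.47 to 0.72 instead of the reported 0.18 to 0.39). There is no cost to the primary analysis, alpha or sample size.
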